6.1.4.2 Prior and concomitant medications (non-MG therapy)

A non-MG related medication is defined by the “indication” value on the Prior and Concomitant Medication eCRF form not equal to “Therapy for MG”.

Past, Prior, Baseline, Concomitant or Concomitant Only medications will be summarized on the SS. Medications will be presented in alphabetical order by Anatomical Main Group (ATC Level 1), then by Pharmacological Subgroup (ATC level 3) and finally by decreasing frequency of PT. In the case of ties, sort these alphabetically. Summaries will include the overall number and percentage of participants receiving at least one treatment of a PT.

Medications classified as past, prior, baseline, concomitant or concomitant only will be listed using the SS. A by-participant listing of concomitant procedures will also be listed using the SS. Originally reported dates will be used for listings.

A by participant listing of Neisseria Meningitidis Vaccination and Prophylaxis will be provided in the SS.

6.1.4.3 MG Specific Prior and Concomitant Medications

MG specific medication will be presented separately from the other prior and concomitant medications (for both tables and listings). A MG specific medication is defined by the “indication” value “Myasthenia Gravis” on the Prior and Concomitant Medication eCRF form. MG specific Past, Prior, Baseline, Concomitant and Concomitant only medications will be summarized on the SS as defined in Section 6.1.4.2.

Additionally, the number and percentage of participants who are taking one or more of the sets of MG specific medications presented in Table 6.2 (i.e., Groups A-H) will be summarized using the same 2 sets of tables: MG specific prior medications and MG specific medications taken at baseline.

Table 6.2: Medication class

Group	Medication	Preferred Term on Prior/Concomitant eCRF form	Reported Term on gMG Treatment History Form
A	Prednisone for gMG	PREDNISONE	PREDNISONE
	Other corticosteroids for gMG	DEXAMETHASONE METHYLPREDNISONE METHYLPREDNISONE SODIUM SUCCINATE PREDNISOLONE METHYLPREDNISOLONE HYDROCORTISONE TBD**	OTHER CORTICOSTEROIDS PREDNISOLONE METHYLPREDNISOLONE
B	Azathioprine	AZATHIOPRINE	AZATHIOPRINE
	Mycophenolate	MYCOPHENOLATE MOFETIL	MYCOPHENOLATE MOFETIL

Table 6.2: Medication class

Group	Medication	Preferred Term on Prior/Concomitant eCRF form	Reported Term on gMG Treatment History Form
		MYCOPHENOLATE ACID	
C	IVIG	IMMUNOGLOBULINS	INTRAVENOUS IMMUNOGLOBULIN
	SCIG	IMMUNOGLOBULINS	SUBCUTANEOUS IMMUNOGLOBULIN
D	PLEX* or Plasmapheresis	PLASMA EXCHANGE PLASMAPHERESIS	PLASMA EXCHANGE PLASMAPHERESIS
E	Cyclosporine	CICLOSPORIN	CYCLOSPORINE
	Cyclophosphamide	CYCLOPHOSPHAMIDE	CYCLOPHOSPHAMIDE
	Methotrexate	METHOTREXATE	METHOTREXATE
	Tacrolimus	TACROLIMUS	TACROLIMUS
	Rituximab	RITUXIMAB	RITUXIMAB
		TBD**	
F	Cholinesterase inhibitors	GALANTAMINE	GALANTAMINE
		PYRIDOSTIGMINE PYRIDOSTIGMINE BROMIDE	PYRIDOSTIGMINE
		AMBENONIUM	AMBENONIUM CHLORIDE AMBENONIUM CHLORURE MYTELASE
		NEOSTIGMINE	NEOSTIGMINE METHYLSULFATE NEOSTIGMINE BROMIDE
		DISTIGMINE	DISTIGMINE BROMIDE
G	C5 inhibitors	ECULIZUMAB	ECULIZUMAB
		RAVULIZUMAB	RAVULIZUMAB
H	FcRn	EFGARTIGIMOD ROZANOLIXIZUMAB	EFGARTIGIMOD ROZANOLIXIZUMAB

eCRF=electronic Case Report Form; gMG=generalized myasthenia gravis; IVIG=intravenous immunoglobulin; NOS=not otherwise specified; PLEX=plasma exchange; SCIG=subcutaneous immunoglobulin

*plasma exchange will be on the Procedures eCRF (if concomitant procedure).

**TBD: To be defined: a complete list of corresponding medications and preferred terms will be provided by UCB prior to DBL

6.1.5 Data derivation rules

6.1.5.1 MG Activities of Daily Living score (MG-ADL score)

The MG-ADL is a brief 8-item survey designed to evaluate MG symptom severity. Higher scores are associated with more severe symptoms of MG. A 2-point change in MG-ADL Score is considered clinically meaningful (Wolfe, Herbelin, Nations, Bryan, & Barohn, 1999); (Muppudi, Wolfe, Conaway, & Burns, 2011).

Table 6.3 presents the 8 items with corresponding response scale, each scored on a 0 to 3-point scale (i.e., 0=none, 1=mild, 2=moderate, and 3=severe). 

If a participant is missing a response for one of the 8 individual MG-ADL items, the participant's corresponding item score from the previous MG-ADL assessment will be imputed for the missing item score (and the total score calculated using this imputed value and the non-missing item scores). If the item response is also missing from the previously scheduled MG-ADL, the MG-ADL total score will be set to missing for that visit. If the participant is missing responses to more than one of the 8 items, the MG-ADL total score will be set to missing for that visit.

Table 6.3: MG-ADL Score

6.1.5.2 Quantitative Myasthenia Gravis (QMG) Score

The QMG is a standardized and validated quantitative strength scoring system that was developed specifically for MG. Higher scores are representative of more severe impairment. A change in the QMG Score of 3 points or more may be considered clinically meaningful, in a

typical clinical trial population of MG patients (Barohn, et al., 1998); (Katzberg, Barnett, Merkies, & Bril, 2014).

Table 6.4 presents the scoring scale for the 13 individual assessments, each scored on a 0 to 3-point scale (i.e., 0=none, 1=mild, 2=moderate, and 3=severe). 

If a participant is missing a response for one of the 13 individual QMG items, the participant's corresponding item score from the previous QMG assessment will be imputed for the missing item score (and the total score calculated using this imputed value and the non-missing item scores). If the item response is also missing from the previously scheduled QMG, the QMG total score will be set to missing for that visit. If the participant is missing responses to more than one of the 13 items, the QMG total score will be set to missing for that visit.

Table 6.4: QMG Score

[figure not shown]

Table 6.4: QMG Score

F=female; M=male.

The functional sub-scores for a participant are defined as the total score of the corresponding items (or the value of the item if it is a single score):

If an item response has a missing value, the same method as for the QMG total score for imputing missing values will be used.

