## **9.6 Handling of dropouts or missing data**

For secondary efficacy analyses, missing data will be handled according to the secondary efficacy estimand definition:

- For missing data of participants who discontinue from the study, a missing at random assumption will be used for imputation. This is in relation to the assumption that the participant had remained on their treatment throughout the study.
- For other missing data, the same missing at random assumption as the one used for imputing missing data of participants who discontinue from the study will be applied.

Missing or partial dates for safety evaluations will be imputed and full details of these algorithms will be presented in the SAP. Baseline is defined as the last nonmissing pretreatment measurement (Section 9.2). Therefore, data from the Screening Visit (if available) will be used as Baseline values if data are missing at Day 1.

No further imputations of any other missing data are planned.

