## **9.8 Determination of sample size**

The secondary efficacy estimand will investigate if the Week 12 MG-ADL score is noninferior to the Baseline MG-ADL score with an NI margin of 2. It is assumed that the Week 12 CFB has an SD of 3 and that the true CFB is 0. Given a sample size of 20 study participants, the study has approximately 80% power to detect this, based on a 1-sided alpha of 0.025.

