6.3 Appendix 3: Changes to Protocol-Planned Analyses

The description of compliance has been added.

More precision on the model used for the main secondary endpoint strategy (MMRM followed by a One-Sample t-test on the LS Means) were given.

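### A QMG subscore made of one item is carried forward when that item is missing, which the protocol does not allow for and SAP 6.3 does not declare

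*SAP*

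**What the plan says.** SAP 6.1.5.2 deals with a missing QMG item by last value: the participant's "corresponding item score from the previous QMG assessment will be imputed for the missing item score". Two limits follow, both worded for the total. The total is missing if the same item was also missing at the previous scheduled QMG, and it is missing if more than one of the 13 items is absent.

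The section then defines the functional subscores as the sum of their items, "or the value of the item if it is a single score", and adds: "If an item response has a missing value, the same method as for the QMG total score for imputing missing values will be used". The list of items in each subscore is not visible in the public copy.

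Protocol 9.6 sets out three provisions: a missing-at-random assumption for the secondary efficacy analyses, imputation of partial dates for safety evaluations, and Screening data as a fallback for Baseline. It closes with "No further imputations of any other missing data are planned". Protocol Table 3-1 places change from Baseline to Week 12 in the QMG subscores among the Other efficacy endpoints, and SAP 5.3.2 analyses these descriptively.

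SAP Section 1 says that changes to protocol-planned analyses are recorded in Section 6.3. That section has two entries. One reads "The description of compliance has been added"; the other gives more detail on the MMRM. Item-level imputation is not mentioned.

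**The concern.** For the QMG total, carrying one item forward is a modest scoring convention, because 12 of the 13 items are still observed at that visit. For a single-item subscore the same words mean something else: 0 of 1 items is observed, and the reported result is wholly an earlier measurement.

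The study asks whether disease control holds after the switch to zilucoplan. A reader of a subscore table will take each Week 12 value as measured at Week 12. With the rule as written, some values may be Week 2 measurements, and nothing in SAP 6.3 warns of it. The protocol sentence that covers these endpoints says the opposite of what the SAP does.

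**Working it through.** **Inputs**
- Planned sample size 20 (Protocol 9.8).
- Item range 0 to 3 (Protocol 8.1.1.2).
- Scheduled QMG at Baseline, Week 2 and Week 12, with further QMG at Early Withdrawal and Rescue Therapy Visits (Protocol Table 1-2).
- Number of participants with a missing item: not given, so an assumption.

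**The plan's own figure.** The documents give no number for missing items. The nearest figure is the power of the MG-ADL test: "Given a sample size of 20 study participants, the study has approximately 80% power to detect this, based on a 1-sided alpha of 0.025", where "It is assumed that the Week 12 CFB has an SD of 3 and that the true CFB is 0" and the test is whether Week 12 is "noninferior to the Baseline MG-ADL score with an NI margin of 2". The noncentrality is 2 / (3/√20) = 2.981. With 19 degrees of freedom and one-sided 0.025, the noncentral t gives 80.7%, which agrees. The QMG subscores do not enter this calculation, so nothing below alters it.

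**What the rule does to a single-item subscore.** Write B, W2 and W12 for the item scores.
- Week 2 missing: the filled value is B, so the reported Week 2 change is B − B = 0 by construction.
- Week 12 missing: the filled value is W2, so the reported Week 12 change is W2 − B. This is the Week 2 change, with stability assumed over the remaining 12 − 2 = 10 weeks. It equals 0 only when W2 = B, which is 4 of the 4 × 4 = 16 possible pairs of scores.

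**Direction.** The error at Week 12 is (W2 − B) − (W12 − B) = W2 − W12. Two illustrations on the 0–3 scale:
- B = 1, W2 = 1, W12 = 3: reported 0, true +2. The result looks too good.
- B = 1, W2 = 2, W12 = 0: reported +1, true −1. The result looks too bad.

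The sign depends on the participant's course, so no direction can be stated in advance.

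**Size.** The absolute error for one participant is at most 3, so the error in a mean over 20 is at most 3k/20 for k affected participants:

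| k (assumed) | Largest error in mean, points |
|---|---|
| 1 | 0.15 |
| 2 | 0.30 |
| 3 | 0.45 |
| 4 | 0.60 |

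These are upper bounds on a 0–3 scale. They require every affected participant to move across the whole range in the same direction.

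**An ambiguity in the limit.** The limit of one missing item is stated only for the total. If it is counted over all 13 items, a wholly missed Week 12 QMG is not filled. If it is counted within each subscore, a single-item subscore would be filled even when the entire QMG was missed. The text supports either reading.

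**Protocol against SAP.** The missing-at-random rule in Protocol 9.6 is confined to the secondary efficacy analyses, which are MG-ADL and the QMG total. The subscores fall outside it, so the closing sentence of 9.6 governs them. SAP 6.1.5.2 describes its own rule as imputation.

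**The case against.** The best defence is that item scoring is derivation, not analysis. SAP 6.1.5 is headed as derivation rules, and Protocol 9 and 9.3.2 leave detail to the SAP. The limits also make the case uncommon: if they carry over to the subscores as written for the total, filling needs an attended in-clinic QMG, done by a trained evaluator, with exactly one item unscored. All data are listed, and nothing tested is involved. The point about rarity stands, and it is why the impact is low. The derivation argument does not fully answer the conflict, since the SAP itself calls the step imputation and promises to record departures in 6.3.

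Several stronger readings are tempting and are not supported:
- **That the rule breaches the missing-at-random assumption.** That assumption does not reach the subscores. For the QMG total, SAP 5.3.1.2.2 still applies the MMRM strategy to missing totals, and one carried item of 13 has little effect.
- **That it fills gaps with no change and so favours maintenance, or shrinks the SD.** Zero change from Baseline is forced only at Week 2, while the named endpoint is at Week 12. The direction is unknown, and no effect on the SD has been shown.
- **That it hides respiratory worsening.** This assumes that the respiratory subscore is the forced vital capacity item alone, which the visible text does not show. MG-ADL, which covers respiratory symptoms, is also collected at five post-Baseline visits.
- **That any wholly missing subscore is filled.** A multi-item subscore missing in full exceeds the one-item limit on either count.

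**Conclusion.** The point holds in a narrow form. As written, SAP 6.1.5.2 reports a value for a single-item subscore at a visit where nothing in it was observed. That conflicts with the no-further-imputation sentence of Protocol 9.6 and is not declared in SAP 6.3.

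The consequence is low: an exploratory, descriptive endpoint, no test, no effect on power, and at most 0.15 points on the mean for each affected participant of 20. This rests on two assumptions. At least one subscore must be single-item; the SAP wording provides for that, but the item list is not shown. And some participants must have that item missing; the documents give no rate.

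**What to change.** Make three short edits:
1. In SAP 6.1.5.2, state that a subscore consisting of one item is missing at a visit when that item is missing.
2. In the same place, state that for multi-item subscores the limit of one missing item is counted over all 13 QMG items, so that subscores and total follow one rule.
3. In SAP 6.3, list the remaining item-level carry-forward as a change from Protocol 9.6.

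Leave the rule for the QMG total alone. Setting a Week 2 total to missing because one item is absent would discard 12 observed items in a study of 20, and the gain does not clearly justify that.

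The cost is perhaps one or two fewer values in a descriptive table. A visit may then show a QMG total without one of its subscores, which a table footnote can explain. The edit does not recover the missing measurement; it ensures that a single-item subscore is reported only when it was observed.

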6.1.5.3 Myasthenia Gravis Quality of Life (MG-QoL 15r)

The MG-QOL15r is a 15-item survey that was designed to assess quality of life in patients with MG. Higher scores indicate more severe impact of the disease on aspects of the patient's life (Burns, et al., 2010), (Burns, et al., 2016). The following are the 15 questions and the corresponding response scales, each scored on a 0–2-point scale (0=Not much at all, 1=Slightly, 2=Very Much).

1. I'm frustrated by my myasthenia gravis.
2. I have trouble using my eyes because of my MG (e.g., double vision).
3. I have trouble eating because of my myasthenia gravis.
4. I have limited my social activity because of my myasthenia gravis.
5. My myasthenia gravis limits my ability to enjoy hobbies and fun activities.
6. I have trouble meeting the needs of my family because of my myasthenia gravis.
7. I have to make plans around my myasthenia gravis.
8. I am bothered by limitations in performing my work (include work at home) because of my myasthenia gravis
9. I have difficulty speaking due to my myasthenia gravis.
10. I have lost some personal independence because of my myasthenia gravis (e.g., driving, shopping, running errands)
11. I am depressed about my myasthenia gravis

-
- 12. I have trouble walking due to my myasthenia gravis
 - 13. I have trouble getting around public places because of my myasthenia gravis.
 - 14. I feel overwhelmed by my myasthenia gravis.
 - 15. I have trouble performing my personal grooming needs due to my myasthenia gravis.

The MG-QOL15r total score is the sum of the 15 individual item scores with a range of 0 to 30.

If a participant is missing a response for one of the 15 individual MG-QOL15r items, the participant's corresponding item score from the previous MG-QOL15r assessment will be imputed for the missing item score (and the total score calculated using this imputed value and the non-missing item scores). If the item response is also missing from the previously scheduled MG-QOL15r, the MG-QOL15r total score will be set to missing for that visit. If the participant is missing responses to more than one of the 15 items, the MG-QOL15r total score will be set to missing for that visit.

6.1.5.4 Minimal Symptom Expression (MSE)

MSE is designed to assess how many participants become free or virtually free of MG symptoms as measured by achieving an MG-ADL total score of 0 or 1 on therapy (Vissing, et al., 2020).

6.1.5.5 MGFA Post-Intervention Status (MGFA-PIS)

The MGFA-PIS is a physician-determined assessment of clinical symptoms of MG after initiation of MG specific therapy.

Pharmacologic Remission (PR) is defined as follows: The participant has no symptoms or signs of MG since baseline and continues to take therapy for MG. Participants taking cholinesterase inhibitors are excluded from this category because their use suggests the presence of weakness.

Minimal manifestation is defined as follows: "The patient has no symptoms of functional limitations from MG but has some weakness on examination of some muscles. This class recognizes that some patients who otherwise meet the definition of Complete Stable Remission or PR do have weakness that is only detectable by careful examination." For the purpose of the current study, minimal manifestation will be determined at each timepoint after treatment initiation (rather than after 1 year).

Change in status since baseline (improved, unchanged, worse, exacerbation, or died of MG) will also be determined.

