**Table 3-1: Objectives and estimands/endpoints**

Objectives	Estimands/endpoints
	
 
Population level summary: The mean of the endpoint
 

To evaluate the efficacy of SC ZLP after switching from IV C5 inhibitors on an additional efficacy endpoint in study participants with gMG	
The secondary efficacy endpoint is:
 
 
CFB to Week 12 in the QMG score
 
 
This endpoint will be analyzed following the same estimand structure as defined for the MG-ADL score. The endpoint assessed will change accordingly.

To evaluate safety and tolerability of SC ZLP after switching from IV C5 inhibitors on additional safety measures in study participants with gMG	
The secondary safety endpoints are:
 
 
Incidence of serious TEAEs over the Main Treatment Period
 
Incidence of study withdrawal over the Main Treatment Period
 

Other	
To further explore the efficacy of SC ZLP on additional efficacy endpoints after switching from IV C5 inhibitors in study participants with gMG	
The other efficacy endpoints are:
 
 
Time to first receipt of rescue therapy over the Main Treatment Period
 
Change in SOC therapy medication dose regimen for gMG during the Main Treatment Period
 
Achievement of Minimal Manifestation Status per MGFA-PIS at Week 12 without rescue therapy
 
Achieving MSE, defined as an MG-ADL of 0 or 1 at Week 12 without rescue therapy
 
CFB to Week 12 in QMG subscores: ocular, bulbar, respiratory, limb
 
CFB to Week 12 in MG-QOL15r score
 
MG-ADL score responder rate (responder is defined as achieving <math>\geq</math> 3-point improvement from Baseline [decrease] at Week 12 and not having taken rescue therapy)
 
QMG score responder rate (responder is defined as achieving <math>\geq</math> 5-point improvement from Baseline [decrease] at Week 12 and not having taken rescue therapy)
 

To explore the time needed for administration of SC ZLP	
The other endpoint is:
 
 
Time needed for administration of SC ZLP
 

To explore study participants' treatment satisfaction following the use of SC ZLP	
The other endpoint is:
 
 
CFB to Week 12 in TSQM-9 scores
 

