5 STATISTICAL ANALYSES

5.1 General Considerations

Statistical analysis and generation of tables, figures, participant data listings, and statistical output will be performed using SAS® Version 9.4 or higher. All tables and listings will use Courier New font size 9.

All clinical study data will be presented in participant data listings.

Descriptive statistics will be displayed to provide an overview of the study results. For continuous variables, descriptive statistics will include number of participants with available measurements (n), mean, SD, median, minimum, and maximum. For categorical variables, the number and percentage of participants in each category will be presented. Unless otherwise noted, the denominator for percentages will be based on the number of participants included in the respective analysis set.

Participants with missing data can generally be accounted for using the following approaches:

- For summaries of demographics and Baseline characteristics: summarize percentages based on all participants in the analysis set and include a “Missing” category (corresponding to

participants with missing data for the variable being summarized) as the last row in the list of categories being summarized.

- For summaries of efficacy and safety variables, unless otherwise specified: summarize percentages based only on those participants with observed data for the variable being summarized. As the denominator may be different from the number of participants in the analysis set being considered, the denominator should be displayed in the table. The general format for displaying this will be “n/Nsub (%).”

Unless otherwise noted, all percentages will be displayed to one decimal place. No percentage will be displayed for zero counts, and no decimal will be presented when the percentage is 100%.

For the purpose of the tabulations the lower and upper confidence limits for the percentages will be truncated at 0 and 100% respectively.

For PK concentrations, summary statistics will include geometric mean, geometric coefficient of variation (CV), 95% confidence intervals (CIs) for geometric mean, arithmetic mean, SD, median, minimum, and maximum. All summaries of PK variables will be based on the observed values. No imputation will be used.

Decimal places for descriptive statistics will always apply the following rules:

- “n” will be an integer;
- Mean, SD, and median will use one additional decimal place compared to the original data;

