5.3.2 Other efficacy endpoint analyses

The other efficacy endpoints are:

- Time to first receipt of rescue therapy over the Main Treatment Period
- Change in SoC therapy medication dose regimen for gMG during the Main Treatment Period
- Achievement of Minimal Manifestation Status per MGFA PIS at Week 12 without rescue therapy
- Achieving MSE, defined as an MG ADL of 0 or 1 at Week 12 without rescue therapy
- CFB to Week 12 in QMG subscores: ocular, bulbar, respiratory, limb
- CFB to Week 12 in MG-QOL15r score
- MG-ADL score responder rate (responder is defined as achieving ≥ 3 -point improvement from Baseline [decrease] at Week 12 and not having taken rescue therapy)
- QMG score responder rate (responder is defined as achieving ≥ 5 -point improvement from Baseline [decrease] at Week 12 and not having taken rescue therapy)

The MG-ADL score responder rate will be assessed based only on participants having an MG-ADL score ≥ 3 at Baseline, while the QMG score responder rate will be assessed based only on participants having an QMG score ≥ 5 at Baseline.

All those endpoints will be analyzed using descriptive statistics, as mentioned in the Section [5.1](#).

The time to first receipt of rescue therapy over the Main Treatment Period and over the Overall Treatment Period will be analyzed as time-to-event, using Kaplan-Meier plots.

For the MG-ADL and QMG responder rate the number and percentage of participants who have a reduction (i.e., improvement) of $\geq X$ will be summarized in the mITT at Week 12. The improvement values will start at the maximum level of worsening and will continue to the maximum level of improvement seen in the study. Note this is an extension of the “Achieving a ≥ 3 -point reduction in MG-ADL Score at Week 12 without rescue therapy” and “Achieving a ≥ 5 -point reduction in QMG Score at Week 12 without rescue therapy” endpoints.

Individual line plots with individual values of Total MG-ADL, QMG and MG-QoL15r scores will be created in mITT.

For participants infected with COVID-19 as per the AE page, CFB in QMG and MG-QOL15r score will be listed by visit separately.

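### As worded, the Minimal Manifestation endpoint requires some weakness on examination, so read literally a participant with no limitation and no weakness at Week 12 does not achieve it

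*SAP*

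**What the plan says.** The protocol (Table 3-1) lists the endpoint as "Achievement of Minimal Manifestation Status per MGFA-PIS at Week 12 without rescue therapy". SAP 5.3.2 repeats it as "Achievement of Minimal Manifestation Status per MGFA PIS at Week 12 without rescue therapy". Neither adds 'or better'.

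SAP 6.1.5.5 defines Minimal Manifestation in two parts: "The patient has no symptoms of functional limitations from MG but has some weakness on examination of some muscles". Protocol 8.1.1.4 gives the same definition, including the clause that the patient "has some weakness on examination of some muscles". The SAP then explains that the class exists because "some patients who otherwise meet the definition of Complete Stable Remission or PR do have weakness that is only detectable by careful examination".

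The same SAP section defines Pharmacologic Remission: "The participant has no symptoms or signs of MG since baseline and continues to take therapy for MG". It adds: "Participants taking cholinesterase inhibitors are excluded from this category because their use suggests the presence of weakness". Pharmacologic Remission is not used in any SAP endpoint or responder rule. Complete Stable Remission is named but not defined.

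For efficacy percentages, the general rule in SAP 5.1 is to "summarize percentages based only on those participants with observed data for the variable being summarized". SAP 5.3.2 analyses all the other efficacy endpoints descriptively.

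**The concern.** A success rate should not go down when a participant gets better. The weakness clause is part of the definition, so a participant who moves from Minimal Manifestation to no detectable weakness leaves the numerator and stays in the denominator. The SAP's own explanation of the class places it just short of remission, so the excluded state is the better one.

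The plan's other response endpoints do not behave this way. Minimal Symptom Expression counts an MG-ADL score of 0 or 1 and so includes the best possible score. The MG-ADL and QMG responder definitions are 'at least' thresholds. Minimal Manifestation is the exception. At stake is how one descriptive rate reads: it could understate the share of participants who are free of functional limitation after the switch.

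**Working it through.** The plan gives no expected count or rate for this endpoint, so there is no figure to reproduce. The check is on definitions, followed by an illustration on assumed counts.

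**Step 1: where each kind of participant falls.** Take a participant with no functional limitation at Week 12, no rescue therapy and an observed MGFA-PIS status, and apply the SAP 6.1.5.5 wording literally.

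| Participant at Week 12 | Fits Minimal Manifestation? | Fits Pharmacologic Remission? |
|---|---|---|
| Some weakness on examination | Yes | No (a sign is present) |
| No weakness, no symptoms or signs since Baseline, on therapy, no cholinesterase inhibitor | No | Yes |
| No weakness, taking a cholinesterase inhibitor | No | No (excluded by the cholinesterase sentence) |
| No weakness now, but signs at some point after Baseline | No | No (signs since Baseline) |

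One definition requires weakness and the other requires its absence, so the two cannot overlap. The last two rows fit neither. Row 3 can occur because protocol 6.5.1 allows pyridostigmine.

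**Step 2: numerator and denominator.** Under SAP 5.1, everyone with an observed status is in the denominator. Rows 2 to 4 are therefore in the denominator but, on the literal wording, not in the numerator.

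**Step 3: size.** Let N be the number evaluable, M the number in Minimal Manifestation and W the number with no limitation and no weakness (rows 2 to 4), all without rescue.

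- Planned rate = M/N
- 'Or better' rate = (M + W)/N
- Difference = W/N

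With N = 20 (the planned sample size, SAP Section 3), each weakness-free participant accounts for 1/20 = 5 percentage points. M and W are assumptions, varied over a range that includes W = 0:

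| M | Planned rate | 'Or better', W = 0 | W = 2 | W = 4 | W = 6 |
|---|---|---|---|---|---|
| 4 | 20% | 20% | 30% | 40% | 50% |
| 8 | 40% | 40% | 50% | 60% | 70% |
| 12 | 60% | 60% | 70% | 80% | 90% |

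**Step 4: direction.** Start from M = 8 and W = 0. If one participant improves from Minimal Manifestation to weakness-free, M becomes 7 and W becomes 1. The planned rate falls from 8/20 = 40% to 7/20 = 35%, while the 'or better' rate stays at 8/20 = 40%. A move from symptomatic to Minimal Manifestation still raises the planned rate, so the perverse step is confined to the top of the scale.

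**The case against.** The strongest reply is that the definition belongs to the instrument. Both documents give the Minimal Manifestation text in quotation marks as an MGFA-PIS class, and the proportion in that class is a legitimate, if narrow, summary. That stands, and it is why the class-only count should be kept. It does not make the rate suitable as a measure of achievement.

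A reader might infer that the plan instructs that participants in Pharmacologic Remission be scored as failures. The documents do not go that far. No sentence says how such a participant is scored, the table specifications are in a separate document (SAP Section 1), and protocol 8.1.1.4 does not list Pharmacologic Remission as a recorded category. The sponsor may intend 'or better'. What can be said is that the only written definition, followed literally with the SAP 5.1 denominator, leaves weakness-free participants out of the numerator.

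A reader might also call the rate biased by a definite amount. That needs a target the documents do not state and counts they do not give. Against a target of 'Minimal Manifestation or better', the rate is understated by W/N, and W may be zero.

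Finally, part of the information is available elsewhere. SAP 5.1 calls for counts in each category of a categorical variable and for listings of all clinical data, so remission would be visible if it is collected. Minimal Symptom Expression and the QMG change cover neighbouring ground. This limits the harm but does not correct the headline rate for this endpoint.

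**Conclusion.** The point holds as a defect of wording in a descriptive endpoint. As written in both documents, a participant with no functional limitation and no weakness at Week 12 does not meet the definition, although the outcome is better than the one that counts. The effect is an understatement of 5 percentage points per such participant at N = 20, relative to an 'or better' rate. It can only be downward, and it is nil if nobody is weakness-free. The table in the working rests on assumed counts and is not a forecast.

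It might seem that counting Minimal Manifestation or Pharmacologic Remission would close the gap. It would not. Weakness-free participants on a cholinesterase inhibitor, and those who had signs after Baseline but none at Week 12, would still fit neither class.

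The consequence is small. This is an 'other' endpoint with no test attached, and neither the primary safety endpoints nor the MG-ADL noninferiority test depends on it.

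**What to change.** In SAP 5.3.2 and 6.1.5.5, define the responder as *Minimal Manifestation or better at Week 12 without rescue therapy*, meaning no symptoms of functional limitation from MG, with or without weakness on examination and regardless of cholinesterase-inhibitor use. Tabulate the MGFA-PIS category counts beside it. Record the change in SAP 6.3, because the endpoint is also worded in the protocol.

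The cost is a few sentences in the SAP and some extra table rows. MGFA-PIS is already scheduled at Week 12 (protocol Table 1-2), so no new visit is needed. The case report form is not among the documents, so the sponsor should confirm that it captures the full category and not just Minimal Manifestation yes or no. The small downside is a departure from the protocol's literal endpoint wording. Showing the Minimal Manifestation-only count as well deals with that.

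The same SAP paragraph can be aligned with the protocol at the same time. It has Minimal Manifestation determined at every timepoint after treatment starts, whereas protocol 8.1.1.4 limits it to Week 12, the Early Withdrawal Visit and a Rescue Therapy Visit.
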